3.2 Sample Screening

3.2.1 Basis to Determine Sample and Sample Size

3.2.1.1 Sample Size of Test Performance Verification

$$n = \frac{\left[Z_{1-\alpha/2} \sqrt{P_0(1-P_0)} + Z_{1-\beta} \sqrt{P_T(1-P_T)} \right]^2}{(P_T - P_0)^2}$$

Where, n represents the sample size; $Z_{1-\alpha/2}$ and $Z_{1-\beta}$ are fractions of standard normal distribution, P_0 is the target value of the evaluation indicator, and P_T is the expected value of the evaluation indicator for in vitro diagnostic reagents.

- (1) BRAF gene: According to the results of preclinical studies, the target value of positive coincidence rate between test reagent and contrast reagent is up to 85% with the expected value up to 95%, the minimum sample size of positive control group is estimated to be 78; the target value of negative coincidence rate is up to 85% with the expected value up to 90%, the minimum sample size of negative control group is estimated to be 363 and the minimum overall sample size is 441.
- (2) TERT gene: According to the results of preclinical studies, the target value of positive coincidence rate between test reagent and contrast reagent is up to 85% with the expected value up to 98%, the minimum sample size of positive control group is estimated to be 40; the target value of negative coincidence rate is up to 85% with the expected value up to 90%, the minimum sample size of negative control group is estimated to be 363 and the minimum overall sample size is 403.

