3.2.1.2 Sample Size of Diagnostic Performance Verification

$$n = \frac{\left[Z_{1-\alpha/2} \sqrt{P_0(1-P_0)} + Z_{1-\beta} \sqrt{P_T(1-P_T)} \right]^2}{(P_T - P_0)^2}$$

Where, n represents the sample size; $Z_{1-\alpha/2}$ and $Z_{1-\beta}$ are fractions of standard normal distribution, P_0 is the target value of the evaluation indicator, and P_T is

the expected value of the evaluation indicator for in vitro diagnostic reagents.

Samples with BRAF or TERT mutation detected by the test reagent are considered as positive, and samples without mutation are considered as negative.

The results of pathological examination and clinical diagnosis will be used for comparison method. Those with pathologically confirmed thyroid cancer will be considered as positive, while those without pathologically confirmed thyroid cancer whose clinical diagnosis is non-cancer without surgery will be considered as negative.

According to relevant literature reports and preclinical study results, if the target value of sensitivity for the test reagent and comparison method is up to 50% with the expected value up to 60%, the minimum sample size of positive control group is estimated to be 194. According to previous experience, the proportion of positive diagnosis upon postoperative pathological examination is generally more than 70%. If estimated as 70%, the overall sample size of prospectively enrolled patients is 278. The target specificity value is 80% with the expected value of 90%, the minimum sample size of negative control group is estimated to be 108. If the proportion of negative results obtained from the postoperative pathological examination is estimated as 30%, the overall sample size of prospectively enrolled patients is 360. For the final overall sample size calculated based on sensitivity and specificity, the larger one (360 cases) shall prevail. Considering the estimated dropout rate of 10%, the final actual overall sample size is 400.

It is planned to carry out the trial in at least three clinical sites, with the enrollment of no less than 300 samples at each site. In case of objective reasons, when the sample size is insufficient, appropriate adjustments can be made among the sites to ensure the overall sample size. If the relevant laws and regulations change during the trial, the latest laws and regulations shall prevail, and the number of samples should be statistically significant.

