3.2.2.3 Elimination criteria

- (1) The investigators consider it inappropriate to continue clinical trials, such as samples prepared without following the required procedures.
- (2) Sample with incomplete sample information.
- (3) Samples with DNA extraction not enough to complete the testing of test reagent or comparison method.

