4.3 Positive, Negative and Total Coincidence Rates Between Test Reagent and Comparison Method

For each genetic locus, fourfold tables will be used to calculate the positive and negative coincidence rates, positive and negative predictive values, total coincidence rate and their 95% confidence intervals. Using statistical software, Kappa test is used to determine statistical significance of the two methods.

Table 1 Result Summary of Clinical Trial Comparing Test Reagent and Comparison Method

Test Reagent	Comparison Method		Total
	Positive	Negative	
Positive	A	B	A+B
Negative	C	D	C+D
Total	A+C	B+D	A+B+C+D

Samples with mutant genotype detected are considered as positive, and samples without mutant genotype are considered as negative.

The calculation formula is:

$$\text{Positive coincidence rate} = A/(A+C) \times 100\%$$

$$\text{Negative compliance rate} = D/(B+D) \times 100\%$$

$$\text{Positive predictive value (PPV)} = A/(A+B) \times 100\%$$

$$\text{Negative predictive value (NPV)} = D/(C+D) \times 100\%$$

$$\text{Total coincidence rate} = (A+D)/(A+B+C+D) \times 100\%$$

The calculation formula of 95% confidence interval: $p \pm 1.96 \times [p(1-p)/n]^{1/2}$ (where P represents positive and negative coincidence rates, positive and negative predictive values and total coincidence rate, n presents the sample size. If $p > 0.9$, Wilson score method will be used for correction).

4.4 Sensitivity, Specificity and Total Coincidence Rate of Test Reagent and Clinical Reference Standard

Table 2 Result Summary of Test Reagent and Clinical Reference Standard

Test Reagent	Gold standard		Total
	Positive	Negative	
Positive	A (true-positive)	B (false-positive)	A+B
Negative	C (false-negative)	D (true-negative)	C+D
Total	A+C	B+D	A+B+C+D

Those with pathologically confirmed thyroid cancer will be considered as positive, while those without pathologically confirmed thyroid cancer whose FNA result is non-cancer without surgery will be considered as negative.

The test reagent and comparison method will be compared, but patients who fail to provide follow-up pathological results will not be included in the comparative

statistics of test reagent and clinical reference standard.

The calculation formula is:

$$\text{Sensitivity} = A/(A+C) \times 100\%$$

$$\text{Specificity} = D/(B+D) \times 100\%$$

$$\text{Total coincidence rate} = (A+D)/(A+B+C+D) \times 100\%$$

$$\text{Positive predictive value (PPV)} = A/(A+B) \times 100\%$$

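### The total of 400, named as final, omits the coincidence-rate minima (441 and 403) and conflicts with the site plan's 900; no sentence says which governs

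*Protocol*

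**What the plan says.** Section 3.2.1.1 sizes the comparison with Sanger sequencing. For BRAF it asks for 78 positives, and "the minimum sample size of negative control group is estimated to be 363 and the minimum overall sample size is 441". For TERT it asks for 40 positives and 363 negatives, and "the minimum overall sample size is 403". It makes no allowance for loss and states no BRAF or TERT prevalence.

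Section 3.2.1.2 sizes the comparison with the clinical reference standard. It derives 278 from sensitivity and 360 from specificity, and continues: "For the final overall sample size calculated based on sensitivity and specificity, the larger one (360 cases) shall prevail". It then states: "Considering the estimated dropout rate of 10%, the final actual overall sample size is 400".

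The next paragraph plans at least three sites, "with the enrollment of no less than 300 samples at each site". If recruitment falls short, "appropriate adjustments can be made among the sites to ensure the overall sample size". That overall size is not given as a number there.

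Section 4.6 requires the lower 95% limit to exceed 85% for the positive and the negative coincidence rate of both genes.

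**The concern.** Section 3.2.4 provides in principle for one sample per subject, and the same enrolled samples serve both comparisons, so a single enrolment total has to cover both objectives. The only total described as final and overall is 400, and it was chosen without reference to 441 or 403. It is below both, even before any loss.

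If 400 governs, the four coincidence-rate criteria rest on fewer samples than the protocol itself calls the minimum. Missing any one of the four means agreement is judged not acceptable. If 900 governs, it is wrong to call 400 final, and the clause allowing adjustment among sites has no defined total to protect. A site team or monitor could stop at 400 and claim compliance. The candidate targets differ by a factor of 900/400 = 2.25.

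**Working it through.** **Reproducing the protocol's figures.** The formula in both sample-size sections is n = [Z(1-α/2)·√(P0(1-P0)) + Z(1-β)·√(PT(1-PT))]² / (PT-P0)². Alpha is two-sided 0.05. Power is not stated; of 80% and 90%, only 80% returns all five group sizes.

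| Quantity | P0 | PT | Computed | Stated |
|---|---|---|---|---|
| BRAF positive rate | 0.85 | 0.95 | 78.0 | 78 |
| Negative rate, either gene | 0.85 | 0.90 | 362.8 | 363 |
| TERT positive rate | 0.85 | 0.98 | 39.6 | 40 |
| Sensitivity | 0.50 | 0.60 | 193.8 | 194 |
| Specificity | 0.80 | 0.90 | 107.4 | 108 |

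The totals follow:
- 78 + 363 = 441 and 40 + 363 = 403.
- 194/0.7 = 277.1, so 278; 108/0.3 = 360; 360/0.9 = 400.
- Site plan: 3 × 300 = 900.

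**400 for the diagnostic objective.** 400 × 0.9 = 360 evaluable, giving 360 × 0.7 = 252 cancers (194 needed) and 360 × 0.3 = 108 non-cancers (108 needed). It suffices.

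**400 for the coincidence rates.** With N evaluable samples, both minima are met only if the share of positives lies between n_pos/N and 1 - 363/N.

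| N | BRAF window | TERT window |
|---|---|---|
| 400 | 19.5% to 9.25% (empty) | 10.0% to 9.25% (empty) |
| 441 | 17.7% only | 9.1% to 17.7% |
| 810 (900 less 10%) | 9.6% to 55.2% | 4.9% to 55.2% |
| 900 | 8.7% to 59.7% | 4.4% to 59.7% |

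**Loss for this comparison.** It lies between 0 and the stated 10%. Under section 4.4, "patients who fail to provide follow-up pathological results will not be included in the comparative" statistics against the clinical standard, so missing pathology does not affect the Sanger comparison. But section 3.2.2.3 eliminates "Samples with DNA extraction not enough to complete the testing of test reagent or comparison method", which affects both. At the full 10%, the 360 evaluable samples are fewer than the 363 negatives alone.

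**Power at 400.** Formula power is Φ{[√n·(PT-P0) - 1.96·√(P0(1-P0))] / √(PT(1-PT))}. Exact power sums binomial probabilities over outcomes whose lower limit exceeds 85%, using the protocol's interval (Wald, or Wilson when the estimate exceeds 0.9).

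| Case | n | Formula | Exact |
|---|---|---|---|
| Negative rate, as planned | 363 | 0.80 | 0.86 |
| Negative rate, 400 - 78 | 322 | 0.74 | 0.84 |
| Negative rate, 360 - 78 | 282 | 0.68 | 0.75 |
| BRAF positive rate, as planned | 78 | 0.80 | 0.80 |
| BRAF positive rate, 400 - 363 | 37 | 0.34 | 0.44 |
| TERT positive rate, as planned | 40 | 0.81 | 0.81 |
| TERT positive rate, 400 - 363 | 37 | 0.74 | 0.83 |

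**Smallest total covering both objectives.** 441/0.9 = 490 at 10% loss. This is a lower bound, because samples are enrolled prospectively without selection on mutation status, and 441 works only at a 17.7% BRAF share. As an assumption only, BRAF shares of 25% and 45% would need 363/0.75 = 484 and 363/0.55 = 660 evaluable, or 538 and 734 enrolled at 10% loss.

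**The case against.** The best defence is that 400 is only a diagnostic subtotal. It stands under the diagnostic heading, and the sentence before it limits the choice to sensitivity and specificity. On this reading 441, 403 and 400 are separate floors. The site paragraph, which comes last and is the only operational instruction, sets a floor of 900 that satisfies them all. The protocol's expected values imply a pooled positive share of 0.7 × 0.6 + 0.3 × 0.1 = 45%. Even if BRAF accounted for all of that, it would lie inside the BRAF window at 900, with or without 10% loss.

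This reading is plausible, but the protocol does not state it. The words final, actual and overall point the other way. The per-site minimum may itself be adjusted, and that clause protects a total without a number.

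On size, part of the defence stands. The component sums are correct. The TERT shortfall without loss is 3 samples, and exact power does not suffer (0.83 against 0.81). For BRAF without loss, exact power for the negative rate is still 0.84. The 0.34 figure arises only if BRAF positives are as few as 9.25%. The 80% benchmark is inferred. These points limit the loss of power but do not reconcile the totals.

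**Conclusion.** The concern holds. The protocol names 400 as its final overall size, but 400 is below its own minimum totals for criteria on which the trial can fail, and it conflicts with a site plan of at least 900. At 400 the two group minima cannot both be met for either gene at any prevalence. With 78 BRAF positives kept, power for the negative rate falls to 0.74 (no loss) or 0.68 (10% loss) by the formula, against 0.80; the exact values are 0.84 or 0.75, against 0.86. The diagnostic objective is not affected. If 900 governs, power for the coincidence rates is not at risk so long as prevalence lies in the windows shown, and the remaining fault is the label on 400.

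The incompatibility of the totals rests on the protocol's figures alone. The power figures also assume the protocol's expected rates, and loss between 0 and 10%. This must be corrected, because the enrolment target is wrong or undefined as written.

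**What to change.** State one overall enrolment target in section 3.2.1, as the maximum over both objectives after loss. For each gene, use max(n_pos/prevalence, n_neg/(1 - prevalence))/(1 - loss). State the assumed BRAF and TERT prevalences and the loss expected in the Sanger comparison. Set the results beside the diagnostic 360/0.9 = 400. At 10% loss the target cannot be below 490.

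Label 400 as the diagnostic minimum, align the target with the per-site minimum, and name it as the total that adjustment among sites must secure. The 900 already written can serve if the stated prevalences lie in the windows above; a TERT prevalence of at least 4.9% is the condition to check. The choice of total is the sponsor's. If 400 is kept, restate the coincidence-rate group sizes and the power they give.

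The cost is protocol wording. If 900 governs, no patients are needed beyond the per-site minimum already planned. If 400 was intended, the cost is at least 490 - 400 = 90 more samples, or a lower stated power.

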3.2.2 Inclusion, exclusion and elimination criteria

3.2.2.1 Inclusion criteria

- (1) Patients with clinically suspected of thyroid cancer who underwent fine needle aspiration (FNA)

- (2) Samples should have appropriate basic clinical information, including: The patient's unique traceable number, age, sex, pathological diagnosis results, etc.
- (3) Subjects who can provide a complete FNA sample
- (4) Subjects who agreed to provide follow-up information

3.2.2.2 Exclusion criteria

Those who do not meet any of the above inclusion criteria will be excluded.

3.2.2.3 Elimination criteria

- (1) The investigators consider it inappropriate to continue clinical trials, such as samples prepared without following the required procedures.
- (2) Sample with incomplete sample information.
- (3) Samples with DNA extraction not enough to complete the testing of test reagent or comparison method.

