3.1 Overall Study Design

3.1.1 Detection performance validation of test reagent

This trial will be conducted in accordance with the principles of the synchronous blind method. The selected cases will be coded, and the selected samples will be detected with the test reagent and comparison method (Sanger sequencing). When the comparison results are inconsistent with the detection results of Sanger sequencing method, the detection results of sanger will be acceptable.

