3.1.2 Performance validation of test reagent

Among the enrolled patients, postoperative pathological results will be obtained from those who underwent surgery subsequently. Those with pathologically confirmed thyroid cancer will be considered as positive, while those without pathologically

confirmed thyroid cancer whose clinical diagnosis is non-cancer without surgery will be considered as negative. The results of the test reagents will be compared and the clinical sensitivity and specificity of the test reagents will be calculated.

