4.1 General Principles of Statistical Analysis

SAS 9.4 or above software will be used for statistical analysis. The sample size is calculated with PASS16. The statistical analysis of the validity and accuracy of test results is based on full analysis set (FAS) and per protocol set (PPS), and the safety analysis is based on safety set (SS). All statistical tests will be conducted on both sides and $P \leq 0.05$ will be considered statistically significant. (Unless otherwise specified)

The quantitative variables are expressed as mean, standard deviation, median, minimum, maximum, lower quartile (Q1) and upper quartile (Q3), while the categorical variables are expressed as the number and percentage of each category.

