4.6 Clinical Evaluation Standard

1) Coincidence rate: Compared to the comparison method, if the lower limit of two-sided 95% confidence interval for both positive and negative coincidence rates of BRAF and TERT genes are greater than the 85% of preset target value, the statistical hypothesis is valid and in good agreement with the comparison method; otherwise, the statistical hypothesis is invalid, and the agreement with comparison method is not acceptable.

2) Sensitivity and specificity: Compared to the clinical reference method, if the lower

limit of two-sided 95% confidence interval for the sensitivity of BRAF or TERT gene pooled detection is greater than 50% of the preset target value and the lower limit of two-sided 95% confidence interval for the sensitivity of BRAF or TERT gene pooled detection is greater than 80% of the preset target value, the statistical hypothesis is valid and the diagnostic accuracy is acceptable; otherwise the statistical hypothesis is invalid, and the diagnostic accuracy is not acceptable.

5 Quality Control Method

Quality control should be applied at every stage of the clinical trial to ensure that all data are reliable and correct. The quality control method is as follows:

- (1) Qualifications of researchers involved in the study Researchers involved in the clinical trial must have professional expertise, qualifications and competences in the clinical trial, and pass the qualification examination, and staffing should be relatively fixed.
- (2) Training and preliminary tests: The sponsor is responsible for the training of researchers before the start of clinical trial, so as to help clinical researchers fully understand the clinical trial protocol, the detection of investigational products, the filling of original records and forms, etc.
- (3) Laboratory quality control: Clinical laboratories should be strictly in accordance with the *Measures for the Administration of Clinical Gene Amplification Testing Laboratories in Medical Institutions* (MOH Office MA [2010] No. 194 or the current effective version) and other relevant administrative regulations of molecular biology laboratories and clinical gene amplification laboratories.
- (4) Only when the quality control of investigational products meets relevant requirements can the test data be valid.

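### The insufficient-DNA elimination rule removes samples from the clinical accuracy analysis because Sanger sequencing lacked DNA, although that analysis does not use Sanger

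*Protocol*

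**What the plan says.** The elimination criteria stand in section 3.2.2, which serves both study objectives. Criterion (3) of section 3.2.2.3 removes "Samples with DNA extraction not enough to complete the testing of test reagent or comparison method". It is not limited to either objective.

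The two objectives need different data:

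- Detection performance (section 3.1.1): "the selected samples will be detected with the test reagent and comparison method (Sanger sequencing". Both DNA-based results are required.
- Clinical performance (section 3.1.2): "The results of the test reagents will be compared and the clinical sensitivity and specificity of the test reagents will be calculated". The reference is pathology, or clinical diagnosis where there was no surgery.

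Section 4.4 does contain an exclusion written for one comparison only: "patients who fail to provide follow-up pathological results will not be included in the comparative" statistics against the clinical reference. Such patients stay in the comparison with Sanger. Criterion (3) carries no matching limit.

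For the clinical analysis, kit results have two classes (section 3.2.1.2): "Samples with BRAF or TERT mutation detected by the test reagent are considered as positive, and samples without mutation are considered as negative". The fourfold table in section 4.4 has no place for a sample that could not be tested.

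**The concern.** A rule that suits the agreement analysis is applied to an analysis that does not need it. Kit-versus-Sanger agreement cannot be computed without a Sanger result, so removing Sanger-insufficient samples from section 4.3 is unavoidable. Sensitivity and specificity in section 4.4 do not depend on whether Sanger could be run. A patient with a valid kit result and a confirmed diagnosis nevertheless leaves both analyses.

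Two things are at stake. Usable diagnostic data are lost, including from the non-cancer group, where the sample-size calculation has no slack. The clinical estimates also become conditional on the DNA demand of a laboratory method that has no role in them. Whether that shifts the estimates is unknown, but the selection is avoidable.

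**Working it through.** **1. Which comparison method does the rule mean?** The protocol uses the term twice. Section 3.1.1 uses it for Sanger. Section 3.2.1.2 uses it for the clinical reference: "The results of pathological examination and clinical diagnosis will be used for comparison method". Criterion (3) concerns the amount of extracted DNA. Pathology and clinical diagnosis are not run on extracted DNA, so only Sanger fits.

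**2. Who is lost from section 4.4?**

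| DNA enough for kit | DNA enough for Sanger | Reference known | Needed for 4.3 | Usable for 4.4 | Under criterion (3) |
|---|---|---|---|---|---|
| yes | yes | yes | yes | yes | kept |
| yes | no | yes | cannot be used | **yes** | **eliminated** |
| no | either | yes | cannot be used | no kit result | eliminated |

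The second row is the defect.

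**3. The plan's own sample size (section 3.2.1.2).** The printed formula, with two-sided 0.05 and 80% power (assumed, since no power is stated), gives:

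- Sensitivity, 50% against 60%: (1.96 × 0.5 + 0.8416 × 0.4899)² / 0.10² = 193.85, so 194.
- Specificity, 80% against 90%: (1.96 × 0.4 + 0.8416 × 0.3)² / 0.10² = 107.43, so 108.
- 194 / 0.7 = 277.1, so 278; 108 / 0.3 = 360; 360 / 0.9 = 400.

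All match the protocol. The arithmetic is not at fault; the question is which samples enter the denominators.

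**4. Data lost to Sanger alone.** The rate is not given, so a range is assumed.

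- 1% of 400 = 4 patients.
- 5% of 400 = 20 patients, about 14 cancers and 6 non-cancers at 70/30.
- The 10% dropout allowance is not split by cause. If other losses use it up and 5% more are lost to Sanger, 400 × 0.85 = 340 remain: 238 cancers (above 194) and 102 non-cancers (below 108).
- Power for specificity at 102 is Φ[(0.10 × √102 − 1.96 × 0.4) / 0.3] = Φ(0.75), about 77%, against 80% at 108.

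**5. Possible shift in sensitivity from Sanger-only losses.** Let a share g of cancers be lost this way, with kit sensitivity s in them and 60% in those kept. Sensitivity over both groups is 0.60 × (1 − g) + s × g. With g = 10% (assumed), s = 30% gives 57% and s = 60% gives 60%. If s exceeded 60%, the combined figure would exceed 60%. The documents give neither g nor s.

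**6. Secondary: samples with too little DNA for the kit.** Let a share f of samples be affected (assumed) and count them all as incorrect. With the interval formula of section 4.4:

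- Sensitivity: 0.60 × (1 − f) = 57.0% at f = 5% and 54.0% at f = 10%. At 194 cancers the lower limits are 57.0 − 7.0 = 50.0% and 54.0 − 7.0 = 47.0%, against 60.0 − 6.9 = 53.1% at f = 0.
- Specificity: 0.90 × 0.95 = 85.5% at f = 5%. At 108 non-cancers the lower limit is 85.5 − 6.6 = 78.9%, against 90.0 − 5.7 = 84.3% at f = 0.
- If such samples were instead counted as showing no mutation, specificity would rise: 0.90 × 0.90 + 0.10 = 91% at f = 10%.

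These figures show only that the counting convention matters. They do not measure the Sanger defect.

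**The case against.** The strongest reply has four parts.

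- **Analysis sets may resolve it.** Section 4.1 says the accuracy analysis "is based on full analysis set (FAS) and per protocol set (PPS"), and neither set is defined in the protocol. A statistical analysis plan could keep an eliminated sample in the full analysis set. This stands as far as the counting of untestable samples goes. It does not remove the main point, because the protocol itself states an elimination rule and exempts no analysis from it.
- **A common sample set may be deliberate.** Section 2 combines the two evaluations, and inclusion criterion (3) already asks for a complete FNA sample. But combining conclusions does not require identical denominators, and section 4.4 already departs from a common set for missing pathology.
- **The loss may be small.** An assumed 5% fits within the 10% dropout allowance if other losses leave room. Section 3.2.1.2 also plans at least three sites with no fewer than 300 samples each, adjustable between sites, which would far exceed 400. This stands for precision. More patients would not undo the selection.
- **No bias is shown.** This stands. The documents do not link DNA yield to cancer status or to mutation detection.

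A reader might infer that the trial measures accuracy only in DNA-rich aspirates, that kit failures in general are dropped, and that the reported figures are therefore inflated. The text does not support this. Criterion (3) requires only enough DNA for both methods and sets no yield threshold. It covers insufficient DNA, not other invalid runs. Those are touched only by a quality-control statement in section 5, "Only when the quality control of investigational products meets relevant requirements can the test data be valid", which contains no elimination rule. Too little DNA may also reflect sampling or extraction rather than the kit.

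**Conclusion.** The point holds in a limited form. Criterion (3) is right for section 4.3 and wrong for section 4.4 in its Sanger part: as written, it discards valid kit results with a known reference diagnosis for a reason unrelated to clinical accuracy. This is a stated rule that misfits one objective, not a detail left for the analysis plan.

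The certain consequence is lost data, at 4 patients for each 1% of 400, with the non-cancer group the first to fall short of its planned size. The possible effect on sensitivity is modest under the assumptions tried (57% to 60% against 60%, with 10% of cancers lost), and its sign is not fixed by the documents. The larger shifts in the worst-case calculation concern samples with too little DNA for the kit, rest on assumed rates, and should not be read as the size of this defect.

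**What to change.** - **Main change, in section 3.2.2.3.** State that insufficient DNA for Sanger removes a sample from the agreement analysis in section 4.3 only. State in section 4.4 that every sample with a valid kit result and a reference diagnosis is included, whether or not Sanger could be run.
- **Secondary addition, in the protocol or the analysis plan.** Report the number of samples with too little DNA for the kit by reference status (cancer, non-cancer, unknown). Add one sensitivity analysis of section 4.4 that counts them as incorrect in both groups, labelled worst case, with the counting convention stated.

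The cost is about one sentence in each of the two sections and one extra table. No new samples or tests are needed. The worst-case figures may be slightly less favourable than the main ones. The denominators of sections 4.3 and 4.4 will differ, so the report should show how each was reached.
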